10.3. Analysis of microbiota and whole genome sequencing

Patients will be stratified into groups according to types and duration of antibiotic exposure. Shotgun metagenomics approach can be used to characterise microbial community dynamics in the respiratory and intestinal tract. The characteristics of the microbiota will be determined by comparing alpha and beta diversity metrics between the groups of patients and healthy volunteers to explore the short- and long-term impact of the various durations of antibiotics in individual patients. The data will also be used to assess if alterations in the repertoire of antibiotic resistant genes can be detected, and to study shifts in functional and metabolic capacity during the time course with a view to getting mechanistic insights into potentially protective components of the microbiome.

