4. OBJECTIVES AND OUTCOME MEASURES

Objectives	Outcome Measures	Timepoint(s) of evaluation of this outcome measure (if applicable)
Primary Objective To demonstrate clinical non-inferiority, followed by superiority, of a shorter antibiotic treatment duration compared to a longer duration in adult patients with VAP	Difference in the proportion of participants with the composite endpoint of death and VAP recurrence rate within 60(± 5) days of enrolment	All outcome measures will be assessed within day 60(± 5) of enrolment
Secondary Objectives To define other clinical benefits of shorter antibiotic treatment duration compared to a longer duration in adult patients with VAP	Ventilator-associated events, duration of mechanical ventilation, duration of hospitalisation, acquisition of multidrug resistant infection or colonisation during the hospitalisation, number of days of exposure to antibiotics during hospitalisation, number and types of extrapulmonary infections during hospitalisation (determined from cultures taken from sterile sites), difference in the proportion of participants with primary outcome in subgroups of patients with VAP caused by Gram-negative non-fermenters and carbapenem-resistant bacilli	All outcome measures will be assessed within day 60(± 5) of enrolment
To study the impact of various antibiotic regimen on the microbial community dynamics and diversity in the respiratory and intestinal tracts in individual patients in order to understand colonisation and transmission of MDROs, identify potentially protective components of the microbiome against MDROs	Characteristics of the microbiota will be determined by comparing alpha and beta diversity metrics between the groups of patients, alterations in the repertoire of antibiotic resistant genes, shifts in microbiota functional and metabolic capacity	Respiratory and stool samples will be collected from the study participants within 24 hours of enrolment, weekly during hospitalisation, and at day 28 (± 5) and 60(± 5) after enrolment

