The 2016 IDSA/ATS VAP guideline recommends a 7-day course of antimicrobial therapy for the treatment of VAP [3]. However, 7-day course is empirical and durations shorter than 7 days have been studied in randomised trials. One of these studies by Singh et al [33] evaluated 3 days of empirical ciprofloxacin monotherapy for patients who satisfy a set of clinical criteria signifying low likelihood of active VAP at day 3 of treatment. Compared to those who received longer duration of antibiotics, there was no difference in mortality or ICU length of stay. Patients in the short duration group had less antibiotic resistance and fewer superinfections. Another randomised study by Micek et al [34], adopted an antibiotic discontinuation policy to shorten VAP treatment. Similarly there was no difference between the short (6.0 ± 4.9 days) and long duration treatment groups in terms of mortality and VAP recurrences. The majority of the causative pathogens in this study are Gram-negative bacteria including *Pseudomonas* and *Acinetobacter*, which are also the commonest VAP pathogens in Asia [34]. The above evidence supports the use of a set of clinical stability criteria to establish the duration of antibiotic treatment for VAP.

The set of clinical stability criteria used in this study is adopted from Micek et al [34], and IDSA/ATS consensus guidelines on the management of community-acquired pneumonia in adults [35]. The community-acquired pneumonia guideline is used because a similar set of clinical stability criteria was not defined in the IDSA/ATS VAP guideline.

Group 2: Long Duration arm

Participants in the control (long duration) arm will receive standard care, which is antibiotic treatment for at least 8 days with the exact duration decided by the primary physician.

Sample and data collection

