6. PARTICIPANT IDENTIFICATION AND RECRUITMENT

6.1. Study Participants

Adult patients (≥ 18 years old) in participating wards who have been on mechanical ventilation for more than 48 hours.

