beta diversity metrics between the groups of patients to explore the short- and long- term impact of the various durations of antibiotics in individual patients. The data will also be used to assess if alterations in the repertoire of antibiotic resistant genes can be detected, and to study shifts in functional and metabolic capacity during the time course with a view to getting mechanistic insights into potentially protective components of the microbiome.

These isolates will be de-identified and stored for up to 15 years for use in future ethically approved studies. We will seek permission from the participants to store their samples and include this in the informed consents.

c) Bacterial isolates from other routine clinical cultures such as blood, cerebral spinal fluid, pus etc

All bacterial isolates including MDR *Acinetobacter spp*, *Pseudomonas spp*, *Enterobacteriaceae*, *Staphylococcus aureus* and *Enterococcus spp*, grown from other routine clinical cultures will be de-identified and stored for up to 15 years for use in future ethically approved studies. In the current study, these isolates will undergo whole genome sequencing to compare the within-host evolution of resistant organisms. We will seek permission from the participants to store their samples for up to 15 years in the informed consents.

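### Protocol 10.3 addresses the microbiome effect of antibiotic duration by exposure received rather than by randomised arm, and names a healthy-volunteer comparator that the trial does not enrol

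*Protocol*

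**What the plan says.** The microbiome is listed among the secondary objectives in the protocol synopsis and in Protocol 4: "To study the impact of various antibiotic regimen on the microbial community dynamics and diversity". The only section that says how these data will be analysed is Protocol 10.3, Analysis of microbiota and whole genome sequencing (the interim analyses carry the same section number). Three parts of it matter here.

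- Grouping: "Patients will be stratified into groups according to types and duration of antibiotic exposure".
- Comparison: "comparing alpha and beta diversity metrics between the groups of patients and healthy volunteers".
- Purpose: "to explore the short- and long-term impact of the various durations of antibiotics in individual patients".

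The section mentions neither the randomised arms nor an analysis population, and it names no covariates.

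Protocol 10.1 states a general rule: primary and secondary outcomes are analysed with and without adjustment, in both the intention-to-treat and the per-protocol population. The SAP's list of secondary objectives (2.1, items a to g) does not include the microbiome, SAP 8.2 to 8.8 do not cover it, and SAP 9.1 plans no further exploratory analysis.

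On sampling, Protocol 4 says: "Respiratory and stool samples will be collected from the study participants within 24 hours of enrolment, weekly during hospitalisation", and again around days 28 and 60. On enrolment, Protocol 6.1 describes one population: "Adult patients (≥ 18 years old) in participating wards who have been on mechanical ventilation for more than 48 hours".

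**The concern.** Part of the microbiome objective is a question about duration, and duration is the one factor this trial allocates at random. A comparison by arm would answer that question with the protection of randomisation. Section 10.3 instead forms groups from what each patient went on to receive. Such groups can differ in illness severity, organism, later infection and survival, each of which could plausibly relate to microbial diversity and resistance genes as well as to days of antibiotics.

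At stake is how this secondary objective is interpreted. If 10.3 is followed literally, a difference between exposure groups may be reported as an effect of duration when the design of that comparison cannot show one. A volunteer comparator with no defined source adds a second uncertainty: nobody can tell from the protocol where those data would come from or how they would be made comparable.

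**Working it through.** The plan gives no effect size, standard deviation, sample count or power for the microbiome objective, so there is no figure to reproduce. The check compares what the sections say.

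**1. Is received duration randomised?** No. Allocation is 1:1 to short or long (Protocol 7.4), but the days actually received depend on later events:

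- In the long arm the course is "antibiotic treatment for at least 8 days with the exact duration decided by the primary physician" (Protocol 5).
- In the short arm the stopping day depends on culture results and clinical stability, and persistent pneumonia or a new infection extends treatment (Protocol 8).
- Antibiotics may be restarted for clinical reasons (SAP 5.5). Section 10.3 does not say whether exposure means the index course or the total over follow-up. If it means the total, restarts count.
- A patient must survive to accumulate a long exposure, and the protocol expects 55% to die or have a recurrence (Protocol 10.2, The Number of Participants).

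**2. Which way would this push the result?** Slow recovery and restarts place sicker patients in the long-exposure groups. Early death places some of the sickest in the short-exposure groups. These oppose each other, and the documents do not say how strongly severity relates to days received or to diversity. Neither the sign nor the size of the net confounding can therefore be derived.

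**3. Would the planned covariates remove it?** Section 10.3 names none. The list in Protocol 10.1 (site, age, comorbidities, SOFA score, haemodynamics on the day of randomisation and so on) describes patients up to randomisation. It would help with baseline differences but does not capture what happens afterwards, which is what lengthens or truncates exposure.

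**4. Does another section supply the randomised comparison?** Only by inference. The microbiome is listed as secondary, so the rule in 10.1 could be read as covering it. But the specific section prescribes different groups and does not refer back, and the SAP never applies the rule to these data. By contrast, SAP 8.7 compares acquisition of resistant organisms by treatment arm, so the plan already uses the randomised comparison for a closely related endpoint.

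**5. Volunteers.** Protocol 10.3 compares patients with healthy volunteers. The nearly identical sentence in Protocol 7.7 has only "beta diversity metrics between the groups of patients to explore", and the synopsis and Protocol 4 also compare groups of patients only. Eligibility (6.1 to 6.3), consent (7.3), sampling (5, 7.5 to 7.7) and the schedule (Appendix B) make no provision for volunteers, and no external data set is named.

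**The case against.** The strongest reply has three parts.

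First, Protocol 10.1 covers secondary outcomes in general and the microbiome is one of them, so a comparison by arm may already be intended. This stands in part: a reader who inferred that the protocol excludes a randomised comparison would go further than the text allows. What remains is that 10.3 sets out different groups and that neither document says how the two sections fit together.

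Second, the objective concerns regimens as well as durations. Antibiotic type is left to the physician (Protocol 8) and is not randomised, so grouping by exposure is the only way to study it. This stands fully. The criticism is confined to duration, and exposure groups remain legitimate if labelled observational and adjusted.

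Third, the section is exploratory in tone, the SAP does not bind later exploratory work (SAP 1), and neither the primary result nor the comparison of resistant-organism acquisition is touched. This also stands and limits the weight of the point. It does not make exposure groups a sound basis for statements about duration.

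Two further readings are tempting but unsupported. A reader might infer that the enrolment sample, taken before randomisation with antibiotics possibly already running, biases a comparison by arm. It does not: exposure before randomisation is balanced between arms in expectation, so this affects precision only. A reader might also infer that a comparison by arm would be free of bias. The documents do not support that either. Death and discharge remove later samples, and Protocol 7.6 lets a telephone interview replace a visit, which yields no specimen. Patients with samples are therefore selected after randomisation in either analysis.

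**Conclusion.** The concern holds for the duration part of the microbiome objective. As written, Protocol 10.3 answers a question about the randomised factor with groups formed after randomisation, and neither the general rule in 10.1 nor the SAP is carried into the section to correct this. Differences between such groups cannot be attributed to duration.

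No magnitude is given. Any figure would need assumed correlations between severity, days received and diversity, and the documents supply none of them. The conclusion rests on two points: received duration depends on clinical course, as the plan's own rules make it do, and clinical course may be related to the microbiota. If the second were untrue, the exposure comparison would not be confounded by this route, but the plan offers no reason to assume so.

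The volunteer comparator is a separate inconsistency of wording within the protocol and has nothing to do with confounding. The point deserves correction before the microbiome data are compared. It does not bear on the primary endpoint.

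**What to change.** In Protocol 10.3 (Analysis of microbiota and whole genome sequencing):

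1. State that the main comparison for duration is short versus long arm as randomised, in the intention-to-treat population, consistent with Protocol 10.1.
2. Adjust that comparison for each patient's last available sample before randomisation, for precision. Given weekly sampling and randomisation within days 0 to 7 (SAP 2.7), this will usually be the enrolment sample.
3. Report by arm how many patients contribute a sample at each time point, with the reasons for absence (death, discharge, telephone follow-up), and discuss what that selection implies.
4. Keep the grouping by antibiotic type and duration received as a secondary analysis, labelled observational, adjusted for the baseline covariates in 10.1, with the exposure window defined.
5. Reconcile the volunteer comparator with the synopsis, Protocol 4 and Protocol 7.7: delete it, or name the external source.

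The cost is wording. No new patients, samples or assays are needed. Keeping the volunteer comparison would require the sponsor to identify and describe an existing data source.

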10.4. Health economics modelling

To assess the implementation cost, we will develop a logic model to describe the experience at each site to specify 'inputs', 'activities', 'outputs' and 'outcomes' arising from a policy of shortening duration of treatments. This will be developed with the site teams and managed by the research team

for consistency in language and definitions. This exercise will provide an opportunity to identify the incremental resources required for the new policy. We expect most of the extra costs to be staff time, but there might be some other consumable or equipment costs. We will use qualitative methods to elicit information from local administrators and health services leaders.

To assess the changes to costs arising directly from the new policy, we will use the trial data on lengths of stay, use of antibiotics, use of other consumables; and, tests and diagnostics. Unit costs will be sought from local administrators or shadow prices imputed where necessary. Data on adverse events associated with ICU stay will be assessed and augmented with information from the literature about how any unobserved adverse events change with ICU duration in similar populations. The costs of these events measured by excess length of stay will also be harvested from the literature; as will estimates of changes to risk of death and health related quality of life, measured by preference-based utility tools.

The data we assemble will be organised in a decision tree or state-based model to capture chance events or frequently recurring events. For the economic modelling, the parameters that describe costs, health outcomes and probabilities will be fitted to prior uncertain distribution and simulation studies completed to propagate forward uncertainties to joint posterior distributions of change to costs and health benefits. Results will be presented as incremental cost-effectiveness ratios and rearranged as a net monetary benefits framework to show the probability that adoption of the novel model of care is cost-effective. Plausible thresholds for valuing health benefits will be used for each country. A probability that adoption is cost-effective that exceed 50% means a rational and risk neutral decision maker will adopt. Not adopting in this situation has a lower chance of being the best decision. The perspective of the health service will be adopted for this evaluation and good practice guidelines for reporting cost-effectiveness will be met.

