10.2. The Number of Participants

The study is designed to demonstrate the non-inferiority, followed by superiority, on the composite endpoint of mortality and recurrence at 60(± 5) days of the short duration versus the long duration of antibiotic treatment for VAP. A meta-analysis showed that mortality attributable to VAP ranges from 13.6–42.8% in Southeast Asia [42]. Considering that our primary outcome is a composite binary outcome of mortality and recurrence of VAP, we estimate this to be 55%. We derived an absolute non-inferiority margin of 12% with the fixed-margin method, preserving at least 50% of the efficacy of standard treatment in VAP. Using a group sequential design adopting the boundaries proposed by Fleming- Harrington- O'Brien ($R=0.8$) [40], a maximum of 412 patients will be required to achieve a power of 80% to conclude non-inferiority between the two groups with an one-sided α risk of 5%. As we anticipate a loss to follow-up of up to 10%, we plan to enrol a maximum of 460 patients.

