8.9. Resource Use and Cost Data

A separate analysis plan for the health economics analysis will be written by the trial health economist. Resource use and cost data will only be assessed for the final analysis, but not for the interim analysis.

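### Protocol 10.4 credits a risk-neutral decision maker with a 50% probability rule, but risk neutrality turns on expected net benefit, and the two rules can disagree if the net-benefit distribution is skewed

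*Protocol*

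**What the plan says.** Protocol 10.4 (Health economics modelling) plans a decision-analytic model with uncertain parameters and "simulation studies completed to propagate forward uncertainties to joint posterior distributions of change to costs and health benefits". Two summaries follow. "Results will be presented as incremental cost-effectiveness ratios", and these are then "rearranged as a net monetary benefits framework to show the probability that adoption of the novel model of care is cost-effective". On the value placed on health, "Plausible thresholds for valuing health benefits will be used for each country"; no figure is given.

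The adoption rule comes next: "A probability that adoption is cost-effective that exceed 50% means a rational and risk neutral decision maker will adopt". Its justification is: "Not adopting in this situation has a lower chance of being the best decision".

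Expected (mean) net benefit is not named as a criterion, and no distributional shape is assumed. SAP 8.9 does not restate or correct the rule: "A separate analysis plan for the health economics analysis will be written by the trial health economist".

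**The concern.** A risk-neutral decision maker, by definition, ranks options by expected payoff, which here is expected incremental net monetary benefit. The plan's rule ranks them by the chance of being the better option. Its second sentence is true as a statement of probability: if adopting is better with probability above 50%, not adopting is better with probability below 50%. But that does not lead to the risk-neutral choice, because it ignores how large the gains and losses are. It also rules out reading the 50% rule as shorthand for expected value.

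At stake is the interpretation of one secondary objective, the change in costs and QALYs from implementing shorter treatment. The model's mean could point one way and the written rule the other, and the plan would have committed to the rule while giving a reason that supports the mean.

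**Working it through.** **Inputs.** From Protocol 10.4: the 50% rule, simulated joint uncertainty in cost and health changes, and country thresholds without figures. From Protocol 10.2 (The Number of Participants), used only in step 5: a 55% event risk and 412 patients, so 412/2 = 206 per arm. The documents give no cost, QALY or threshold values, so every money and QALY amount below is assumed. The distributions stand for uncertainty about *mean* net benefit, not spread between patients.

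**Notation.** B = λ × (QALY change) − (cost change), for adopting against not adopting, with λ the threshold per QALY. The plan's rule is P(B > 0) > 0.5, that is, median B > 0. The risk-neutral rule is E[B] > 0. The 50% is stipulated, so there is no figure to reproduce; the question is when it matches E[B] > 0.

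**1. Symmetric case.** B normal with SD 2,000, so P = Φ(mean/2,000). Means of −500, −100, 0, 100 and 500 give P = 0.401, 0.480, 0.500, 0.520 and 0.599. The rules agree throughout.

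**2. Two outcomes.** Gain G with probability p, loss L otherwise: E[B] = pG − (1 − p)L.

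| p | G | L | E[B] | 50% rule | Risk-neutral |
|---|---|---|---|---|---|
| 0.60 | 1,000 | 2,000 | 600 − 800 = −200 | adopt | reject |
| 0.90 | 1,000 | 10,000 | 900 − 1,000 = −100 | adopt | reject |
| 0.40 | 3,000 | 1,000 | 1,200 − 600 = +600 | reject | adopt |

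Break-even is L/G = p/(1 − p). At p = 0.60, adoption is an expected loss once the loss exceeds 0.60/0.40 = 1.5 times the gain. The third row shows the error running the other way.

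**3. Fixed saving, skewed harm.** B = a − X, with X lognormal (median m, log-SD σ). Then P = Φ(ln(a/m)/σ) and E[B] = a − m·exp(σ²/2). With a = 400, m = 300, σ = 1.2: P = Φ(0.2877/1.2) = 0.595, and E[B] = 400 − 300·exp(0.72) = 400 − 616 = −216. The largest P compatible with E[B] ≤ 0 is Φ(σ/2), which is 0.550, 0.599 and 0.691 for σ = 0.25, 0.5 and 1.0.

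**4. Uncertain saving, skewed QALY loss.** One million draws, with a gamma saving (mean 1,000), a lognormal QALY loss (median 0.02, log-SD 1.2) and λ = 30,000. Result: P = 0.656 and E[B] about −235. The closed form for the mean is 1,000 − 30,000 × 0.02 × exp(0.72) = −233.

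**5. How wide could the disagreement be at this trial's size?** Steps 2 to 4 use values that produce disagreement. As a less selective check, take beta uncertainty on event risk with 206 per arm and 55% in the long arm, a lognormal QALY loss per event with mean 2 and coefficient of variation 0.25 to 1.0, and an SD of 1,000 on the mean saving. Set the mean saving so that E[B] = 0. The P at that point marks how far from 50% the two rules can part.

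| λ per QALY | Excess risk, short arm | P when E[B] = 0 |
|---|---|---|
| 3,000 | 0 to 4 points | 0.50 to 0.51 |
| 30,000 | 0 to 2 points | 0.50 to 0.58 |
| 30,000 | 4 points | 0.52 to 0.63 |

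The 0.63 needs a coefficient of variation of 1.0.

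**The case against.** The best defence is that the rules will usually agree. The model propagates uncertainty about population means, and skew between patients largely averages out in a mean difference. Nor is the composite event rare: at 55% with 206 per arm the risk difference has SD √(2 × 0.55 × 0.45/206) = 0.049 and is almost symmetric. Step 5 shows a narrow band of disagreement under many settings. This stands as a limit on size. It does not make the sentence correct, because uncertain QALY losses and literature-based inputs can still skew the product, and nothing in the plan assumes they will not.

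The cost-effectiveness ratios are a partial remedy. If computed as ratios of mean changes and compared with the threshold, they carry the expected-value answer. But the plan does not tie adoption to them. The commitment to good reporting practice does not alter a stated decision rule either.

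The separate health-economics plan may state the rule properly. It is not among these documents, so that remains unknown.

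A reader might go further in three ways, none of which the documents support:

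- *Net benefit will be skewed because lengths of stay are.* That confuses spread between patients with uncertainty about the mean.
- *The error always favours adoption.* The third row of step 2 shows the reverse, and skewed savings from shorter stays would push that way.
- *Adoption advice for each country is a stated objective.* The objective in Protocol section 4 is to estimate changes in costs and QALYs. Country enters Protocol 10.4 only through the thresholds.

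**Conclusion.** The point holds as a matter of logic: the 50% criterion is a median rule presented as a risk-neutral one, and a single counterexample is enough to show that the two differ. If uncertainty in mean net benefit is skewed, the written rule can support adoption at an expected loss or reject an expected gain.

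The size is not determinable from the documents. Assumed examples give disagreement at probabilities from 0.40 to 0.90. The assumed model at this trial's sample size confines it to between 0.50 and at most 0.63, often to almost nothing. If net benefit is close to symmetric, the rules coincide. The non-inferiority conclusion and the clinical secondary analyses do not depend on this rule. It is a misstatement in a secondary, model-based analysis, worth correcting because the correction is nearly free.

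**What to change.** In Protocol 10.4, replace the 50% sentence and the one after it with:

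> Adoption is supported if expected incremental net monetary benefit at the country threshold is above zero; the probability of cost-effectiveness is reported as a measure of decision uncertainty.

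Carry the same rule into the separate health-economics plan named in SAP 8.9. The cost is a short text change in each document. No new data or modelling is needed, because the mean comes from the simulation draws already planned.
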